### **11 ADVERSE EXPERIENCE REPORTING AND DOCUMENTATION**

#### **11.1 Adverse Events**

An adverse event (AE) is any untoward medical occurrence in a clinical investigation of a patient administered a pharmaceutical product and that does not necessarily have a causal relationship with the treatment. An AE is therefore any unfavorable and unintended sign (including an abnormal laboratory finding), symptom or disease temporally associated with the administration of an investigational product, whether or not related to that investigational product. An unexpected AE is one of a type not identified in nature,

severity, or frequency in the current Brochure or of greater severity or frequency than expected based on the information in the Investigator's Brochure.

The Investigator will probe, via discussion with the subject, for the occurrence of AEs during each subject visit and record the information in the site's source documents. Adverse events will be recorded in the patient CRF. Adverse events will be described by duration (start and stop dates and times), severity, outcome, treatment and relation to study drug, or if unrelated, the cause.

### AE Severity

The National Cancer Institute's Common Terminology Criteria for Adverse Events (CTCAE) Version 3.0 should be used to assess and grade AE severity, including laboratory abnormalities judged to be clinically significant. The modified criteria can be found in the study manual. If the experience is not covered in the modified criteria, the guidelines shown in Table 1 below should be used to grade severity. It should be pointed out that the term "severe" is a measure of intensity and that a severe AE is not necessarily serious.

**Table 1. AE Severity Grading**

Severity (Toxicity Grade)	Description
Mild (1)	Transient or mild discomfort; no limitation in activity; no medical intervention or therapy required. The subject may be aware of the sign or symptom but tolerates it reasonably well.
Moderate (2)	Mild to moderate limitation in activity, no or minimal medical intervention/therapy required.
Severe (3)	Marked limitation in activity, medical intervention/therapy required, hospitalizations possible.
Life-threatening (4)	The subject is at risk of death due to the adverse experience as it occurred. This does not refer to an experience that hypothetically might have caused death if it were more severe.

### AE Relationship to Study Drug

The relationship of an AE to the study drug should be assessed using the following the guidelines in Table 2.

**Table 2. AE Relationship to Study Drug**

Relationship to Drug	Comment
Definitely	Previously known toxicity of agent; or an event that follows a reasonable temporal sequence from administration of the drug; that follows a known or expected response pattern to the suspected drug; that is confirmed by stopping or reducing the dosage of the drug; and that is not explained by any other reasonable hypothesis.

Probably	An event that follows a reasonable temporal sequence from administration of the drug; that follows a known or expected response pattern to the suspected drug; that is confirmed by stopping or reducing the dosage of the drug; and that is unlikely to be explained by the known characteristics of the subject's clinical state or by other interventions.
Possibly	An event that follows a reasonable temporal sequence from administration of the drug; that follows a known or expected response pattern to that suspected drug; but that could readily have been produced by a number of other factors.
Unrelated	An event that can be determined with certainty to have no relationship to the study drug.

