### 11.2.1 Serious Adverse Experience Reporting

Study sites will document all SAEs that occur (whether or not related to study drug) per [UCSF CHR Guidelines](#) and those outlined in 21CFR312.32. The collection period for all SAEs will begin after informed consent is obtained and end after procedures for the final study visit have been completed.

This study is investigator-sponsored and does not involve any outside sponsoring institution to which adverse events should be reported. Serious Adverse Events (SAEs) or unanticipated adverse events, therefore, will be reported to the FDA CDER (Center of Drug Evaluation and Research), as well as internally to the UC San Francisco Committee on Human Research (CHR), within respective reporting guidelines.

Unexpected fatal or life-threatening suspected adverse reactions will be reported to the CDER no later than 7 calendar days after initial receipt of the information. UCSF CHR will be notified within 10 working days of the event's occurrence.

Per 21 CFM 312.32(c)(1), any (1) serious, unexpected suspected adverse reactions, (2) findings from other clinical, animal, or in-vitro studies that suggest significant human risk, and (3) a clinically important increase in the rate of a serious suspected adverse reaction will be reported to the CDER no later than 15 calendar days after determining that the information qualifies for reporting.

All adverse events during this study will be recorded in real time in UCSF's HIPAA approved clinical database, REDCap. Recording such events in the same database as each patient's trial-based visit records will allow for more efficient tracking and monitoring of all adverse events within the study.

In accordance with the standard operating procedures and policies of the local Institutional Review Board (IRB)/Independent Ethics Committee (IEC), the site investigator will report SAEs to the IRB/IEC as described above.

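### Table 2 offers no valid causality grade for an adverse event that is new in kind and not certainly unrelated, and is not reconciled with the expedited reporting rules in Section 11.2.1

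*Combined protocol and SAP*

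**What the plan says.** Section 11.1 gives one instruction for causality: "The relationship of an AE to the study drug should be assessed using the following the guidelines in Table 2". That table has four grades.

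- *Definitely* opens with two routes: "Previously known toxicity of agent; or an event that follows a reasonable temporal sequence from administration of the drug". The second route goes on to require an event "that follows a known or expected response pattern to the suspected drug; that is confirmed by stopping or reducing the dosage of the drug", with no other reasonable explanation.
- *Probably* repeats the timing, pattern and stopping conditions, and asks that other explanations be unlikely.
- *Possibly* drops the stopping condition but keeps the pattern condition. After plausible timing it asks for an event "that follows a known or expected response pattern to that suspected drug; but that could readily have been produced by a number of other factors".
- The last grade, *Unrelated*, is defined as "An event that can be determined with certainty to have no relationship to the study drug".

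There is no grade for unlikely, unknown or not assessable.

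Expectedness is defined in the opening text of Section 11.1: "An unexpected AE is one of a type not identified in nature", with severity and frequency as further grounds, judged against the Brochure.

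Section 11.2.1 then sets two clocks for individual cases. The first reads: "Unexpected fatal or life-threatening suspected adverse reactions will be reported to the CDER no later than 7 calendar days", counted from when the report first comes in. The second gives 15 calendar days for reactions that are serious, unexpected and suspected. The section cites 21 CFR 312.32. It neither defines a suspected adverse reaction nor says which Table 2 grades count as one.

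**The concern.** Expectedness and causality are separate questions, and the two clocks in Section 11.2.1 need a yes to both. Table 2 merges them by making prior knowledge of the reaction a condition of every related grade. The events that the expedited rules most need to catch, those new in kind, are then the events that the scale cannot grade.

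Two things are at stake. One is the prompt FDA report of a novel serious reaction. The other is the adverse event tabulation by relationship to study drug in Section 15.4, which serves the second and third key secondary objectives in Section 3.2 (tolerability and safety in this population).

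The setting gives this some weight. The safety trials cited in Sections 1.2 and 2 are not described as including MS patients, and Section 4.1 lets participants stay on their disease-modifying treatment. Section 14 dispenses with a DSMB and leaves safety monitoring and reporting to the investigator. Section 15.5 mentions a committee that follows serious events, but does not say that it reviews causality grades.

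**Working it through.** No arithmetic applies; the plan gives no figure on this point. The check reads each row of Table 2 as a set of conditions that must all be met, and tests one kind of event against it.

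**Test event.** (a) Timing after dosing is plausible. (b) It is not a previously known toxicity. (c) It follows no known or expected pattern for the drug. (d) A link to the drug cannot be ruled out with certainty.

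| Grade | Deciding condition | Result |
|---|---|---|
| Definitely, first route | Toxicity already known | Fails, by (b) |
| Definitely, second route | Known or expected pattern | Fails, by (c) |
| Probably | Known or expected pattern | Fails, by (c) |
| Possibly | Known or expected pattern | Fails, by (c) |
| Unrelated | Certainty of no link | Fails, by (d) |

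The event fits 0 of 4 grades. All 3 related grades require prior knowledge of the reaction. The alternative route in *Definitely* does not help, because it too requires a known toxicity.

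**Against the reporting rules.** If the nature of the event is not in the Brochure, Section 11.1 makes it unexpected. To start the 7- or 15-day clock it must also be suspected. On the literal wording of Table 2 it cannot be graded as related, so the two conditions cannot both be met by way of that table. An event that is unexpected only in severity or frequency can still follow a known pattern and be graded. The gap is therefore confined to events new in kind.

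**Routes that do not depend on a grade.**

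- Section 11.2.1 has all serious events documented whether related or not.
- Section 11.2.1 also has a general sentence sending serious or unanticipated events to the FDA and the local committee. It has no causality filter, but it refers to the respective guidelines and sets no clock of its own.
- Section 17.2 sends serious events to the IRB whatever the cause.
- Section 17.5, item 8, requires prompt reporting of unanticipated problems involving risk to the IRB and the FDA.
- Section 5.3.7 gives the local committee 10 working days and names no FDA route.

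A novel serious event would therefore not go unreported under the protocol. None of these routes secures the 7- or 15-day timing, and none supplies a grade for the Section 15.4 table. For a novel event that is not serious, the expedited clocks do not apply and the main exposure is the Section 15.4 table.

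**The case against.** The best reply is that nothing in the protocol makes a Table 2 grade the gate to expedited reporting. Section 11.1 calls the table guidelines, and Section 11.2.1 takes its standard from the cited regulation and never mentions the table. An investigator could judge *suspected* directly from the regulation. This stands. A reader might infer that the table blocks the FDA report of a novel reaction; the documents do not support that. They support a risk that the clock is missed, because the only causality tool they supply gives no answer.

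A reader might also infer that such events would be filed as *Unrelated* and so bias the Section 15.4 table downward. This is not shown. *Unrelated* requires certainty, and Section 11.1 asks for a cause to be recorded when an event is called unrelated. A rater could as easily choose *Possibly* or leave the field empty. The net direction is unknown.

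A third inference is that the stopping-or-reducing condition shuts deaths out of expedited reporting, since a death cannot be confirmed that way. It limits access to *Probably* and to the second route of *Definitely*, but *Possibly* does not require it, so it adds nothing to the reporting argument.

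Finally, *expected* could be read loosely to take in any pharmacologically plausible response. That narrows the gap but leaves an event that is truly new in kind without a grade.

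**Conclusion.** The point holds as a defect of wording with a limited consequence. Table 2 is not exhaustive, and it makes prior knowledge a condition of relatedness while Sections 11.1 and 11.2.1 rely on events that are both unexpected and suspected. The exposure is a risk, not a certainty, of missing the 7- and 15-day clocks, together with ungraded or arbitrarily graded events in the Section 15.4 table.

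Its size is 0 of 4 grades for this class of event. How many such events will occur cannot be known in advance, and no particular event can be named as an instance because the Brochure is not among the documents.

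The conclusion assumes that the table is applied as written. Section 11.3, Medical Monitoring, is listed in the contents but was not in the text available for this review, so nothing is concluded about any escalation route there.

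**What to change.** 1. Reword Table 2 so that every event has a grade. In *Possibly*, make a known or expected pattern a supportive feature and not a required one.
2. Record expectedness as a separate judgment against the Brochure, using the Section 11.1 definition.
3. Reconcile Table 2 with Section 11.2.1 by stating which grades count as a suspected adverse reaction. Take the threshold from 21 CFR 312.32, which the protocol already cites. That text is not in the documents, so the sponsor should check the final wording against it.

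The cost is one table and the matching case report form field. The downside is small: somewhat more events graded *Possibly*, and perhaps a few more reports.

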## 11.2 Serious Adverse Experiences (SAE)

An SAE is defined as any AE occurring at any dose that results in any of the following outcomes:

- death
- a life-threatening adverse experience
- inpatient hospitalization or prolongation of existing hospitalization
- a persistent or significant disability/incapacity
- a congenital anomaly/birth defect

Other important medical events may also be considered an SAE when, based on appropriate medical judgment, they jeopardize the subject or require intervention to prevent one of the outcomes listed.

### 11.2.1 Serious Adverse Experience Reporting

Study sites will document all SAEs that occur (whether or not related to study drug) per [UCSF CHR Guidelines](#) and those outlined in 21CFR312.32. The collection period for all SAEs will begin after informed consent is obtained and end after procedures for the final study visit have been completed.

This study is investigator-sponsored and does not involve any outside sponsoring institution to which adverse events should be reported. Serious Adverse Events (SAEs) or unanticipated adverse events, therefore, will be reported to the FDA CDER (Center of Drug Evaluation and Research), as well as internally to the UC San Francisco Committee on Human Research (CHR), within respective reporting guidelines.

Unexpected fatal or life-threatening suspected adverse reactions will be reported to the CDER no later than 7 calendar days after initial receipt of the information. UCSF CHR will be notified within 10 working days of the event's occurrence.

Per 21 CFM 312.32(c)(1), any (1) serious, unexpected suspected adverse reactions, (2) findings from other clinical, animal, or in-vitro studies that suggest significant human risk, and (3) a clinically important increase in the rate of a serious suspected adverse reaction will be reported to the CDER no later than 15 calendar days after determining that the information qualifies for reporting.

All adverse events during this study will be recorded in real time in UCSF's HIPAA approved clinical database, REDCap. Recording such events in the same database as each patient's trial-based visit records will allow for more efficient tracking and monitoring of all adverse events within the study.

In accordance with the standard operating procedures and policies of the local Institutional Review Board (IRB)/Independent Ethics Committee (IEC), the site investigator will report SAEs to the IRB/IEC as described above.

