SAFETY EVALUATIONS	
Phone call at week 6 to see if patient is experiencing any unacceptable side effects.
 
When approximately 50% of patients have completed the study through Study Visit 2 (total visit 3), an interim analysis for safety will be conducted by the PI. Serious adverse events will be monitored by the committee on an ongoing basis throughout the study.
 
Incidence of adverse events.

PLANNED INTERIM ANALYSES	When approximately 50% of patients have completed the study through Study Visit 2 (total visit 3), an interim analysis for safety will be conducted by the PI. Serious adverse events will be monitored by the committee on an ongoing basis throughout the study.
STATISTICS Primary Analysis Plan	Data will be analyzed per protocol utilizing an intention to treat approach including all patients randomized to the study for the principal analysis. Loss to follow up will be accounted for using standard statistical methods. The principal analysis will be performed using mixed effects linear regression model controlling for clustering by eye.
Rationale for Number of Subjects	
With 25 patients per group the study has 90% power to detect a 50% relative reduction in latency with BZA compared to placebo at the 3-month outcome for group 1 assuming a two-sided test with alpha = 0.05.
 
Study size may be expanded to compensate for dropouts over the short study period. To maximize study efficiency and resource utilization these subjects will not be enrolled unless necessary.

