### 4 STUDY DESIGN

#### 4.1 Study Overview

This is a 6-month randomized, single center, double blinded, delayed start study in 50 patients with relapsing remitting multiple sclerosis and identified injury to the anterior visual pathway.

Patients will be randomized 1:1 into two groups: Group A and Group B. Group A will receive 180 days of Bazedoxifene while Group B will receive 90 days of placebo followed by 90 days of Bazedoxifene. Patients will receive two fixed oral tablets of 20mg Bazedoxifene (Conbriza) daily (to be taken at the same time). Patients will be permitted to remain on their standard disease modifying treatment during the course of the study.

Screening data will be reviewed to determine subject eligibility. Subjects who meet all inclusion criteria and none of the exclusion criteria will be entered into the study

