### 8.4.1 Dosage/Dosage Regimen

The medication (BZA or placebo) will be taken once daily, in the morning, for the duration of the study (stage 1 = 3 months, stage 2 = 3 months).

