#### **10.4 Visit 4 (6-month)**

1. Record any Adverse Experiences and/or Review subject diary for adverse experiences and dosing compliance.
2. Record changes to concomitant medications.
3. Perform abbreviated physical examination.
4. Assess likely side effects via clinician observation and questionnaires
5. Perform and record vital signs.
6. Collect blood for research laboratory tests (if needed)
7. Perform neurologic and ophthalmologic exam
8. Perform and record visual assessments (OCT, high/low contrast vision testing, cone contrast, VFQ)
9. Perform and record cognitive & other tests (SDMT, MFIS, EDSS, SF-36)
10. Perform timed walking tests (T25W, TUG, 6 min walking test)
11. Perform MRI (no contrast)
12. Collect blood for clinical laboratory tests (chemistry, hematology)

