#### APPENDIX 1. SCHEDULE OF STUDY VISITS

	SCREENING VISIT 1 (Screen) a	STUDY1 VISIT 2 (Baseline) a	STUDY2 VISIT 3 (Month 3) a	STUDY3 VISIT 4 (MONTH 6)
Informed Consent	X			
Medical History	X			
Complete Physical Exam	X			
Abbreviated Physical Exam		X	X	X
Height	X			
Weight	X			
Vital Signs	X	X	X	X
Pregnancy Test (Serum)	X			
Hematology	X		X	X
Chemistry	X			X
Research blood stored	X	X	X	X
Neurological + ophthalmological exam with neurologist		X	X	X

MRI		X	X	X
Randomization	X			
Dispensing of Study Drug		X	X	
Counting of Returned Study Drug				X
Initiate Subject Diary	X			
Subject Diary Review		X	X	X
Concomitant Medication Review	X	X	X	X
Additional cognitive assessments		X	X	X
OCT	X	X		X
VEP	X	X	X	X
Vision testing (high, low contrast)		X	X	X
Cone contrast		X	X	X
VFQ		X	X	X
Questionnaires (MFIS, MSWS12, SF-36)		X	X	X
Assess likely side effects		X	X	X
EDSS		X	X	X
SDMT		X	X	X
Timed walking tests		X	X	X
ERG** (optional)	X			

Safety phone call at Week 6.

\*\* \*\*In rare cases during the initial visit, the patient may be asked to undergo an electroretinogram. This test measures the electrical response of the eye's light-sensitive cells, called rods and cones. These cells are part of the retina (the back part of the eye). This test is used to detect disorders of the retina. For this study, this option exists only to be used in cases where more information is needed to confirm a diagnosis of optic neuritis. The test is performed by placing numbing drops in the patient's eyes, so that there is no discomfort. Then, the patient's eyes are held open with a small device called a retractor. An electrical sensor (electrode) is placed on each eye and the electrical activity of the retina is recorded in response to light. The primary risk associated with the study is a temporary scratch of the surface of the cornea due to the electrode. Otherwise, there are no risks associated with this procedure.

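### SAE collection closes with Visit 4, at about the last daily bazedoxifene dose, and completers have no later scheduled contact, so their planned post-dose SAE window is about 0 days

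*Combined protocol and SAP*

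**What the plan says.** - **SAE period.** Section 11.2.1 starts SAE collection at consent and has it "end after procedures for the final study visit have been completed".
- **Dosing.** Section 4.1: "Group A will receive 180 days of Bazedoxifene while Group B will receive 90 days of placebo followed by 90 days of Bazedoxifene". Section 8.4.1 has study medication taken every morning "for the duration of the study (stage 1 = 3 months, stage 2 = 3 months"). Both groups are therefore on active drug throughout Stage 2.
- **Last visit.** Visit 4 at month 6 is the last visit for completers in Section 10 and the last column of Appendix 1. The Appendix 1 row "Counting of Returned Study Drug" is marked at Visit 4 only.
- **Other contact.** The one scheduled phone contact falls during treatment. Appendix 1 has "Safety phone call at Week 6"; the synopsis has "Phone call at week 6 to see if patient is experiencing any unacceptable side effects".
- **How events are found.** Section 11.1 has the investigator probe "for the occurrence of AEs during each subject visit".
- **Follow-up elsewhere.** Section 12.1 follows a subject withdrawn from treatment because of an adverse event until it settles. Section 14, under withdrawal and stopping rules, requires a Safety Follow-Up visit for a patient who discontinues study medication. That visit has no stated timing and appears in neither Section 10 nor Appendix 1.

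**The concern.** Documenting safety is the third key secondary objective (Section 3.2). Exclusions 22 and 26 to 28 in Section 6.3 show that the protocol takes thromboembolic risk seriously. Yet nobody is scheduled to ask a completer about a hospitalisation or a clot in the days and weeks after the last capsule. Completers include the patients with the longest exposure, 180 days in Group A.

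A second consequence concerns causality. Table 2 in Section 11.1 uses the response to stopping or reducing the drug among its criteria for the two highest grades of relatedness. For a completer with an event still open at Visit 4, no contact is planned at which that response could be observed.

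What is at stake is individual safety follow-up and the completeness of the descriptive safety record.

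**Working it through.** **1. Reproduce the plan's participation limit.** The synopsis allows 200 days per subject. Section 10.1 sets screening to baseline at 14 ± 2 days. Treatment is 180 days (Section 4.1), or six calendar months of about 183 and at most 184 days.

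- Nominal: 14 + 180 = 194 days, leaving 200 − 194 = 6 days.
- Shortest: 12 + 180 = 192 days, leaving 8 days.
- Longest screening with 183 days: 16 + 183 = 199 days, leaving 1 day.
- Longest screening with 184 days: 16 + 184 = 200 days, leaving 0 days.

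The 200-day limit is thus accounted for by screening plus treatment. It contains no planned post-treatment period, and no contact is scheduled in the few days of slack.

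**2. Post-dose window for completers.**

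Window = (end of SAE collection) − (last dose).

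Collection ends with Visit 4 procedures, and daily dosing runs to about Visit 4, so the window is about 0 days. The documents give no window for Visit 4. If drug stops at day 180 and Visit 4 falls at 184 days, the gap is 184 − 180 = 4 days. The slack in step 1 caps it at about 8 days.

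**3. Do other provisions fill the gap?**

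| Provision | Reaches a completer after the last dose? |
|---|---|
| Section 12.1, follow-up after withdrawal for an adverse event | No; only subjects withdrawn from treatment for that reason |
| Section 14, Safety Follow-Up visit | Not clearly; placed with the stopping rules, untimed, not in the schedule |
| Section 9.1.4, new examination findings followed at the next scheduled visit | No; there is no visit after Visit 4 |
| Sections 5.2.2 and 9.1.6, unexpected MRI findings | Partly; a Visit 4 scan finding leads to safety action and adverse event reporting, but not to a post-dose contact |
| Section 14, biweekly staff review | Partly; it can pick up a Visit 4 result, but involves no contact with the participant |

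**4. Time a post-dose interval would cover.** The documents give no interval, so 30 days is assumed, with a range of 14 to 30, 50 patients and no dropout.

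- 30 days: 50 × 30 = 1,500 patient-days; 1,500 / 365.25 = 4.1 patient-years.
- 14 days: 50 × 14 = 700 patient-days; 700 / 365.25 = 1.9 patient-years.

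This is time covered, not harm. With no post-dose event rate in the documents, it cannot be turned into a number of SAEs.

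**The case against.** The case against giving this much weight has real content.

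- **It is a stated choice.** Section 11.2.1 sets an explicit period, and nothing in the protocol requires a post-dose interval. This stands: the point is a design improvement, not a contradiction.
- **No post-dose hazard is shown.** The documents give no half-life, residual-effect period or event rate. Section 1.2 cites large 2- and 3-year trials with 840 and 1,872 women at 40 mg and favourable tolerability, and the exclusions remove the patients at highest thromboembolic risk. A reader might infer that serious events are being missed; the documents do not support that, nor do they rule it out.
- **The information gain is small.** The interval adds at most about 4.1 patient-years. There is no placebo comparator, because both groups have just come off active drug. This stands.
- **The Safety Follow-Up visit is ambiguous.** It applies to discontinuation for any reason and directly follows the definition of study completion, so completers may have been intended. Its place under the stopping rules and its absence from the schedule favour the narrower reading. If the wider one was meant, the text still needs to say so and give a timing.
- **Visit 4 results are not ignored.** The last Visit 4 item is "Collect blood for clinical laboratory tests (chemistry, hematology"), and a reader might infer that nobody looks at the result. Section 14 provides biweekly safety review, and Section 16.1 makes the investigator review all data. No change is needed there.
- **Late events remain reportable.** A reader might infer that an SAE after Visit 4 would go unreported. The reporting duties in Sections 11.2.1 and 17.5 apply once the investigator learns of an event; what is missing is a planned way of learning of it.
- **Some text is unseen.** Section 11.3 (Medical Monitoring), listed in the table of contents, and the institutional guidelines cited in Section 11.2.1 were not available. Either could bear on follow-up after the study.

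**Conclusion.** The point holds for completers. As written, SAE collection stops at about the last bazedoxifene dose in both groups and no later contact is scheduled. The planned post-dose window is about 0 days, at most a few, for up to 50 patients.

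The consequence is modest. It concerns individual follow-up and descriptive safety data, and leaves the primary analysis untouched. It would be wrong to say that patients get no follow-up after stopping: early stoppers have provisions of their own, and unexpected findings on a Visit 4 scan are covered.

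The conclusion rests on the stated end of collection, the visit schedule, and reading the Safety Follow-Up visit as meant for early stoppers. Confidence is medium because of that ambiguity and the unseen text. This is a cheap improvement that should be made, not a flaw that threatens the trial.

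**What to change.** 1. Amend Section 11.2.1 so that SAE collection ends at the later of the final study visit and a fixed interval after the last dose. Thirty days is a working assumption; the sponsor should confirm the interval from the product information.
2. Capture it with one scripted phone call by existing staff, modelled on the Week 6 call, asking about hospitalisation, thromboembolic symptoms and adverse events ongoing at Visit 4.
3. Add the call to Section 10 and Appendix 1, and raise the synopsis limit on participation: 200 + 30 = 230 days (200 + 14 = 214 with a 14-day interval).
4. State in Section 14 whether the Safety Follow-Up visit applies to completers. The call can serve as that contact.

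**Cost.** Up to 50 calls: 50 × 15 / 60 = 12.5 staff hours at an assumed 15 minutes each (8.3 hours at 10 minutes, 25 at 30). One IRB-approved amendment covers all four changes. The main downside is time: study close-out, and release of the randomization worksheet to the investigators (Section 8.2), move about 30 days later, so the planned 24 months become about 25. No new staff or clinical procedure is needed.
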